## 7.13 Long-term Follow-up (Expansion Phase Only)

For a period of 1 year following the safety follow-up visit, subjects treated in the expansion phase will be contacted at least quarterly ( $\pm 1$  week) via routine clinic visit and/or telephone call to assess the following:

- subsequent anticancer therapies
- status of any ongoing/chronic AEs that were treatment-emergent
- persistence of ADA in those subjects who seroconverted
- date of disease progression (if not documented on study)
- survival status

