### *Pseudoprogression or Indeterminate Response*

Some therapeutic agents, particularly immunotherapeutics, display different patterns of anti-tumor response, which may include a period of increasing tumor burden followed by a response, stable disease followed by slow decline in tumor burden, or even a response in the presence of new lesions (Cheson et al., 2016; Chow, 2013; Wolchok et al., 2009). Immune-mediated responses may take longer to manifest than those from cytotoxic agents. In other cancer settings, a phenomenon called “tumor flare” or pseudoprogression has also been described, in which increased contrast enhancement and hyperintensity is observed on posttreatment MRI scans (fluid - attenuated inversion recovery, or FLAIR) which represents a biologic effect on the tumor and its microenvironment and which stabilizes or diminishes over time (Batchelor, 2012).

In order to avoid falsely assigning disease progression during the expansion phase of the study, a subject whose radiologic disease assessment is indicative of progression may, at the discretion of the Investigator and Medical Monitor, be considered “Indeterminate” in the case report forms and continue on treatment pending a repeat scan 4 to 6 weeks later, if all of the following criteria are met:

- absence of symptomatic or clinical progression
- stable performance status
- adequate tolerance to TTI-621 therapy
- treating beyond progression does not delay an intervention felt to be in the subject’s best interest

If the second confirmatory scan indicates unequivocal disease progression, the subject will be discontinued from treatment. The date of the first scan indicating progression will be used for analysis purposes. If however the second scan indicates a reduction in tumor burden or stable disease from the baseline scan, the subject may continue on treatment in the absence of unacceptable toxicity or other reason for treatment discontinuation.

Notwithstanding, the Investigator is free to remove the subject from treatment at any time during the study if it is felt to be in the subject's best interest.

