#### **3.7.1 Overall Response Rate**

For each subject, a disease-specific overall assessment will be made by the investigator. The table below indicates the responder and non-responder CRF categories for each type of malignancy.

Type of Hematologic Malignancy	CRF	CRF variable label	CRF Assessment Categories (* indicates responder category, ** indicates progressive disease category)
Lymphoma (Hodgkin or Non-Hodgkin)	Response Assessment – Cheson Lugano Classification 2014	"Overall Visit Response at This Assessment"	CR*, PR*, SD, PD**, NE

Multiple Myeloma	Response Assessment – IMWG	"Overall Objective Response at this assessment"	CR*, sCR*, VGPR*, PR*, SD, PD**, Clinical Relapse**, NE, NA
Acute Myeloid Leukemia	AML Response Assessment – Cheson 2003	"Overall Objective Response at This Assessment"	Morphologic leukemia-free state*, Morphologic complete remission*, Cytogenetic complete remission*, Molecular complete remission*, Partial Remission*, Treatment Failure, Unknown
Chronic Lymphocytic Leukemia	Response Assessment – Hallek 2008	"Overall Visit Response at This Assessment"	Complete Response or Complete Remission*, Complete Response or Complete Remission with Incomplete Marrow Recovery*, Partial Response*, Relapse or Progressive Disease**, Stable Disease, Unknown
Myelodysplastic Syndrome (RAEB-1 or RAEB-2)	Response Assessment – MDS	"Overall Objective Response at this assessment"	CR: Marrow*, CR*, PR*, SD, PD**, NE, NA

A subject will be considered to be a responder if the subject had at least two consecutive assessments at which the subject is identified as a responder according to the table above. A subject will be considered to have progressive disease if the subject had at least one assessment at which the subject is identified as having progressive disease according to the table above. The earliest of the consecutive dates at which a responder assessment is made will be the Date of Response. The earliest date at which a progressive disease assessment is made will be the Date of Progression.

In the full analysis set and the response evaluable set, the Overall Response Rate (ORR) is defined as follows.

$$ORR = 100 * \frac{\text{Number of responders}}{\text{Total number of subjects}}$$

(Note that subjects having a response of NE, NA, Unknown, or missing are included in the denominator in this calculation and summarized as non-responders.)

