### **3.7.2 Duration of Response and Progression Free Survival Time**

The time-to-event endpoints measured in this study are defined in terms of the following dates.

- Date of first dose = Date of first dose as recorded on Treatment CRF
- Date of response = Earliest of the consecutive dates at which subject is assessed in a responder category
- Date of last non-PD assessment = Date of last non-missing assessment other than NE, NA, or Unknown
- Date of progression = Date at which subject is first assessed as having progressive disease
- Date of initiation of anticancer treatment = Earliest concomitant medication start date for concomitant medications identified by sponsor as being anticancer treatments

- Date of death = Date of death from any cause as recorded on Death Page CRF

The following time-to-event endpoints will be calculated for each subject.

- DOR for subjects who achieved an objective response = Duration of response (in weeks) =  $[\min(\text{Date of progression}) - \text{Date of response} + 1]/7$
- PFS = Progression free survival time (in weeks) =  $[\min(\text{Date of progression}, \text{Date of death}) - \text{Date of first dose} + 1]/7$

In the case of missing dates (ie, subjects without an event), the following censoring rules will be applied.

Endpoint	Censor if:	Censoring date = Minimum of indicated dates		
		Date of last non-PD assessment	Date of initiation of anticancer treatment	Date of death
DOR	Death prior to progression			X
DOR or PFS	Subsequent anticancer therapy is initiated in the absence of documented progression		X	
	Death or progression after $\geq 2$ assessments of NE, NA, Unknown, or Missing	X		
	Alive & progression free	X	X	

DOR and PFS will be displayed in listings.

The number of subjects with event for DOR and PFS will be summarized. Median time to event, the 25th and 75th percentiles of time to event, along with 95% CI for DOR and PFS will be estimated according to the Kaplan-Meier estimate using the Brookmeyer-Crowley method.

Additionally, the PFS rate at selected landmarks (e.g., 6 months) and corresponding 95% CIs will be estimated using the Kaplan-Meier method. Greenwood's formula will be used to calculate the standard errors of the Kaplan-Meier estimate and upper and lower limits of the 95% CI.

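### The SAP lets a PD recorded before a response give a zero or negative duration of response, and gives no role to progression dates collected in long-term follow-up

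*SAP*

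**What the plan says.** **Progression.** SAP 3.7.1 classes a subject as progressed "if the subject had at least one assessment at which the subject is identified as having progressive disease according to the table above"; that table lists response-assessment forms by malignancy. The date is the earliest such PD: "The earliest date at which a progressive disease assessment is made will be the Date of Progression". SAP 3.7.2 repeats this: "Date of progression = Date at which subject is first assessed as having progressive disease".

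**Response.** A responder needs "at least two consecutive assessments at which the subject is identified as a responder" (SAP 3.7.1). The date of response is the "Earliest of the consecutive dates at which subject is assessed in a responder category" (SAP 3.7.2). Neither section requires the response to precede PD, or PD to follow the response.

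**Formulas (SAP 3.7.2).** DOR = (date of progression − date of response + 1)/7. PFS = (earlier of progression and death − first dose + 1)/7. Deaths come from the Death Page, with no end of window.

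**Censoring (SAP 3.7.2).** For DOR, death before progression is censored at the death date. For both endpoints, new anticancer therapy without documented progression is censored at its start. Death or progression after two or more NE, NA, Unknown or Missing assessments is censored at the last non-PD assessment.

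**Protocol.** Section 7.13 collects, at least quarterly for a year after the safety follow-up visit in the expansion phase, the "date of disease progression (if not documented on study"). Section 8.4.6 counts documented recurrence or progression as the event and does not restrict it to on-treatment forms. Section 7.14.1 anticipates "a period of increasing tumor burden followed by a response" and lets the investigator and Medical Monitor enter an apparent radiologic progression as Indeterminate pending a repeat scan.

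**The concern.** There are two gaps.

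1. DOR subtracts the response date from the first PD ever recorded. If that PD came first, the result is zero or negative, which cannot enter a Kaplan-Meier analysis sensibly. The subject still counts in ORR, so the unsettled status of a response after PD also touches responder counts.

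2. Progression dates collected after treatment are neither used nor excluded by the SAP. A subject who stops without PD, progresses in follow-up and then dies may have the PFS event placed at death; one who progresses and survives is censored at the last on-study assessment. For DOR, a responder who progresses in follow-up and then dies, with no new therapy recorded, can be carried as still in response and censored at death.

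PFS and DOR are secondary endpoints in Parts 2 and 3, and DOR also in Part 4. Cohorts are small enough for one mishandled responder to be visible in a DOR summary.

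**Working it through.** The documents give no figure to reproduce here, so the SAP formulas are applied to illustrative dates on the protocol schedule. First dose = day 1; ends of Weeks 8, 16, 24 and 36 = days 56, 112, 168 and 252.

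**PD before response**

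- PD Week 8, response from Week 16: (56 − 112 + 1)/7 = −7.9 weeks.
- PD Week 8, response from Week 24: (56 − 168 + 1)/7 = −15.9 weeks.
- PD Week 16, response from Week 36: (112 − 252 + 1)/7 = −19.9 weeks.
- PD one day before response gives 0; two or more days before gives a negative value.
- In the first case, ending DOR at the next PD at Week 36 gives (252 − 112 + 1)/7 = +20.1 weeks.

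**Progression in follow-up**

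Take a last non-PD assessment on day 112, follow-up progression on day 154, death on day 200 and no new therapy. Only the Week 24 visit (day 168) is missed before death, so the missed-assessment rule does not apply on either reading.

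- PFS on the SAP's literal text: event at 200/7 = 28.6 weeks, or censored at 112/7 = 16.0 weeks if alive.
- PFS using the follow-up date: event at 154/7 = 22.0 weeks.
- DOR if the response began on day 56: censored at (200 − 56 + 1)/7 = 20.7 weeks on the SAP text, against an event at (154 − 56 + 1)/7 = 14.1 weeks using the follow-up date.

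**What limits the deaths that count in PFS**

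If Missing includes scheduled visits not done after treatment ends, the second missed visit falls 16 weeks after a last assessment at Week 8 (Week 24), 20 weeks after one at Week 16 (Week 36), and 24 weeks after one at Week 24 (Week 48). Deaths after that are censored. Follow-up runs about 30/7 + 52.2 = 56 weeks after the last dose. If no visit counts as scheduled after end of treatment, every later death without recorded new therapy is an event.

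**Simulated size**

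These inputs are assumptions, not document figures: median PFS 20 weeks, median survival after progression 40 weeks, 2% per week stopping before PD, protocol visit schedule, 56-week window, 40,000 subjects.

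| Reading of Missing | Risk after stopping | 26-week PFS, SAP text | 26-week PFS, follow-up PD used | Difference (points) |
|---|---|---|---|---|
| Excludes visits after end of treatment | unchanged | 44.5% | 40.3% | +4.2 |
| Excludes | doubled | 44.6% | 35.5% | +9.1 |
| Includes them | unchanged | 40.5% | 40.3% | +0.2 |
| Includes them | doubled | 39.7% | 35.5% | +4.2 |

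With unchanged risk, 52-week PFS is 18% against 13% on the first reading and 15.2% against 13.1% on the second. Subjects with an event number 77% and 65% respectively, against 95% when follow-up PD is used.

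A second set-up with the same inputs and 200,000 subjects gave 44.3% for the SAP text on the first reading. On the second reading it gave 40.4% against 42.4% with follow-up PD used (−2.0 points), and 40.0% against 36.3% (+3.7) with doubled risk. The sign in the unchanged-risk case on the second reading therefore depends on modelling detail.

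**The case against.** **Negative DOR is an edge case.** Treatment normally stops at progression, and a Week 8 increase followed by PR is the pattern that the Indeterminate entry covers. This stands as to frequency. It does not close the gap: the entry is discretionary, it addresses radiologic assessments and so does not clearly cover skin or blood PD in CTCL, and the SAP's lymphoma row (CR, PR, SD, PD, NE) does not say how to treat it.

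**The case report form is not available.** The SAP table is visibly incomplete (no CTCL, ALL or SCLC form), so a category absent from it may exist on the form. The wording in SAP 3.7.2, "Date at which subject is first assessed as having progressive disease", could alone be read to admit follow-up progression. Both points stand. The point is therefore about what the SAP specifies, and two possible readings are a reason to state one.

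**Follow-up dates are softer.** They may come from a telephone call without formal response criteria, and Protocol 8.4.6 leaves progression and censoring dates to the SAP. An on-study-only definition is defensible, but it should be chosen explicitly.

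**A stronger reading to avoid.** A reader might infer that PFS and DOR are overstated even when stopping is unrelated to prognosis, because deaths replace earlier progressions. The documents do not support this. Under the SAP a death is never a DOR event, so it cannot replace a progression there. For PFS, the new-therapy and missed-assessment rules remove some or many later deaths, and if Missing covers visits after end of treatment the 26-week overstatement disappears in the unchanged-risk case.

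**Conclusion.** The point holds in limited form. The stated DOR rule can produce an impossible value, −7.9 weeks in the plainest example. That follows directly from the SAP and needs no assumption beyond a PD recorded before a confirmed response; it should be uncommon.

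The omission of follow-up progression dates is the literal reading of SAP 3.7.1, supported by the SAP's silence rather than by an explicit exclusion. Under the assumed inputs, 26-week PFS is overstated by about 4 points if Missing excludes visits after end of treatment. If it includes them, the difference is roughly nil (+0.2 or −2.0) when stopping is unrelated to prognosis, and about 4 points when progression risk doubles after stopping. On either reading many collected progressions go unused. No general claim that PFS and DOR are overstated is warranted.

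PFS and DOR are secondary and descriptive, and the Simon decisions rest on responder counts. Of the matters raised here, only the handling of a response after PD could change those counts.

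**What to change.** Amend SAP 3.7.1 and 3.7.2 to:

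- end DOR at the first PD or relapse after the date of response;
- state that a response starting after a recorded PD does not count, unless that assessment was entered as Indeterminate and progression was not confirmed;
- say how Indeterminate maps to the response categories and how a later-confirmed progression is dated (Protocol 7.14.1 uses the first scan);
- take the progression date for PFS and DOR as the earliest of form-recorded PD and follow-up progression before new anticancer therapy, subject to the missed-assessment rule, with an on-study-only sensitivity analysis;
- define Missing after end of treatment, and say whether the two assessments must be consecutive, as Protocol 8.4.6 has it.

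The cost is SAP wording and programming; Protocol 7.13 already collects the dates. The downside is that follow-up dates may be less precise, which the sensitivity analysis would show.

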### **3.7.2 Duration of Response and Progression Free Survival Time**

The time-to-event endpoints measured in this study are defined in terms of the following dates.

- Date of first dose = Date of first dose as recorded on Treatment CRF
- Date of response = Earliest of the consecutive dates at which subject is assessed in a responder category
- Date of last non-PD assessment = Date of last non-missing assessment other than NE, NA, or Unknown
- Date of progression = Date at which subject is first assessed as having progressive disease
- Date of initiation of anticancer treatment = Earliest concomitant medication start date for concomitant medications identified by sponsor as being anticancer treatments

- Date of death = Date of death from any cause as recorded on Death Page CRF

The following time-to-event endpoints will be calculated for each subject.

- DOR for subjects who achieved an objective response = Duration of response (in weeks) =  $[\min(\text{Date of progression}) - \text{Date of response} + 1]/7$
- PFS = Progression free survival time (in weeks) =  $[\min(\text{Date of progression}, \text{Date of death}) - \text{Date of first dose} + 1]/7$

In the case of missing dates (ie, subjects without an event), the following censoring rules will be applied.

Endpoint	Censor if:	Censoring date = Minimum of indicated dates		
		Date of last non-PD assessment	Date of initiation of anticancer treatment	Date of death
DOR	Death prior to progression			X
DOR or PFS	Subsequent anticancer therapy is initiated in the absence of documented progression		X	
	Death or progression after $\geq 2$ assessments of NE, NA, Unknown, or Missing	X		
	Alive & progression free	X	X	

DOR and PFS will be displayed in listings.

The number of subjects with event for DOR and PFS will be summarized. Median time to event, the 25th and 75th percentiles of time to event, along with 95% CI for DOR and PFS will be estimated according to the Kaplan-Meier estimate using the Brookmeyer-Crowley method.

Additionally, the PFS rate at selected landmarks (e.g., 6 months) and corresponding 95% CIs will be estimated using the Kaplan-Meier method. Greenwood's formula will be used to calculate the standard errors of the Kaplan-Meier estimate and upper and lower limits of the 95% CI.

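### When a first progressing scan is entered as Indeterminate, the SAP dates confirmed progression to the repeat scan, about 4 to 6 weeks after the date the protocol requires

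*SAP*

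**What the plan says.** **Protocol 7.14.1, Pseudoprogression or Indeterminate Response.** In the expansion phase, a radiologic assessment that points to progression may, if four conditions are met and the investigator and medical monitor choose, be labelled Indeterminate "in the case report forms and continue on treatment pending a repeat scan 4 to 6 weeks later". If the second scan shows unequivocal progression, "The date of the first scan indicating progression will be used for analysis purposes".

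**SAP 3.7.1.** A subject has progressed on the basis of "at least one assessment at which the subject is identified as having progressive disease according to the table above", and "The earliest date at which a progressive disease assessment is made will be the Date of Progression". For lymphoma the table lists CR, PR, SD, PD and NE. No malignancy has an Indeterminate category.

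**SAP 3.7.2.** The definition is repeated: "Date of progression = Date at which subject is first assessed as having progressive disease". For censoring, "Date of last non-PD assessment = Date of last non-missing assessment other than NE, NA, or Unknown". Six months is named as an example PFS landmark.

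The SAP's only use of the term Indeterminate is in 3.5.6, for antibody status. Protocol 8.4.6 speaks of documented progression and does not restate the first-scan rule.

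**The concern.** The two documents give different progression dates for the same subject. The protocol looks back from the confirming scan to the first one. The SAP looks forward to the first entry in a PD category, which is the confirming scan if the first was recorded as Indeterminate. A programmer working from the SAP alone has no text that would produce the protocol's date.

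PFS and DOR are secondary and descriptive, but they are not idle. The protocol synopsis says that how long responses last, and disease control, may influence whether the Part 3 cohorts go to Stage 2. Protocol 8.3 lets long progression-free intervals support expansion of a disease cohort. In single-arm cohorts of 12 to 40 subjects, there is no comparator in which such a shift would cancel.

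**Working it through.** The documents state no sample size, power or error rate that depends on this date rule, so there is no plan figure to reproduce. The check is date arithmetic.

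**Inputs**
- Repeat-scan interval: 4 to 6 weeks, or 28 to 42 days (Protocol 7.14.1).
- Disease assessments: end of Weeks 8, 16 and 24, then every 12 weeks (Protocol 7.9, 7.10).
- Window on response assessments: ±1 week (Protocol 7).
- Six months: 365.25 / 2 / 7 = 26.1 weeks.
- Share of subjects affected: not given. I assume 5% to 30% for illustration only.

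**Formulas (SAP 3.7.2)**
- PFS = (date of progression − date of first dose + 1) / 7
- DOR = (date of progression − date of response + 1) / 7

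**PFS.** First dose is Day 1. An Indeterminate scan at the end of Week w falls on Day 7w, so PFS under the protocol is (7w − 1 + 1) / 7 = w weeks. Under the SAP it is w + 4 to w + 6.

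| First scan | Protocol | SAP | Increase |
|---|---|---|---|
| Week 8 | 8 | 12-14 | 50-75% |
| Week 16 | 16 | 20-22 | 25-37.5% |
| Week 24 | 24 | 28-30 | 16.7-25% |
| Week 36 | 36 | 40-42 | 11.1-16.7% |

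If the ±1 week window also applies to the repeat scan, the shift is 3 to 7 weeks.

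**DOR.** Take a response dated Day 56 and a first progressing scan on Day 168.
- Protocol: (168 − 56 + 1) / 7 = 16.1 weeks.
- SAP, repeat scan on Day 196 to 210: (196 − 56 + 1) / 7 = 20.1 to (210 − 56 + 1) / 7 = 22.1 weeks.

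**Six-month PFS.** A Week 24 scan confirmed at Week 28-30 is an event before 26.1 weeks under the protocol and event-free at 26.1 weeks under the SAP. Ignoring censoring, one such subject moves the rate by 100/n points: 2.9 at n = 35, 5.6 at n = 18, 8.3 at n = 12.

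**Cohort mean PFS.** The shift is the affected share times 4 to 6 weeks: 0.2-0.3 weeks at an assumed 5%, 1.2-1.8 weeks at an assumed 30%.

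**Dependence on how the first scan is stored**

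| Stored as | If progression is confirmed | Otherwise |
|---|---|---|
| Indeterminate, its own value | Dated 4-6 weeks late | Passes the NE/NA/Unknown filter, so can be the last non-PD assessment. With no repeat after Week 24, censoring falls at Week 24, not Week 16 |
| NE | Dated 4-6 weeks late | Counts toward the rule that censors after two or more NE or missing assessments |
| SD | Dated 4-6 weeks late | Can be the last non-PD assessment |
| PD | Date agrees with the protocol | A pseudoprogression that resolves is a PFS event, because one PD entry is enough |

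No row gives the protocol's intended result in both columns.

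**The case against.** The strongest reply is that this is a gap rather than a conflict. The SAP's phrase about when a subject is first assessed with progressive disease can be read together with the protocol's first scan. The two part only if that scan is coded as something other than PD and not updated later. The case report form (version 14.0, per SAP 1) is not available to us, and the lymphoma categories the SAP lists contain no Indeterminate option. This stands in part: the shift is conditional on the coding. But the protocol directs that the scan be considered Indeterminate in the case report forms, neither document calls for later recoding, and the SAP counts only entries in a PD category.

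It can also be said that the protocol leaves final analytical detail to the SAP (Sections 8 and 8.4.6). But the SAP says it is based on protocol version 9.0, its version 2.0 was updated to align with protocol changes, and it declares no departure from the first-scan rule.

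The objection on scope stands. The label is optional and applies only to radiologic progression in the expansion phase. In CTCL, post-screening imaging is limited to visceral lesions seen at screening and to confirming a response (Appendix D Table 3, footnote b). AML, ALL and MDS are assessed by marrow and blood. PTCL and the other lymphomas are more exposed.

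A reader might infer that the SAP rule always favours the drug. The documents do not support that. If the first scan is entered as PD and later resolves, the SAP counts an event that the protocol meant to avoid. If the repeat scan shows stable disease or shrinkage and the first was not entered as PD, no progression date is shifted.

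**Conclusion.** The point holds in conditional form. Where the first scan is recorded as Indeterminate, as the protocol directs, and progression is then confirmed, the SAP gives a date about 4 to 6 weeks later than the protocol requires. This lengthens PFS in Parts 2 and 3 and, in responders, DOR. It can carry a Week 24 progression past the 6-month landmark.

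Two further effects depend on coding. The Indeterminate scan can serve as the last non-PD assessment only if it is stored as something other than NE, NA or Unknown. A resolved pseudoprogression becomes a PFS event only if the scan was entered as PD.

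The number of subjects affected is unknown, so the effect on any cohort's median or landmark rate cannot be stated. A reader might also infer that the Simon decision is compromised. It is not: that rule counts responders and does not use the progression date. The primary safety endpoint is likewise untouched. The SAP should be corrected, but no primary conclusion depends on it.

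**What to change.** Add to SAP 3.7.1 and 3.7.2:

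- **(a)** An Indeterminate assessment followed by confirmed progression is PD, dated to the Indeterminate scan.
- **(b)** An Indeterminate assessment not confirmed as progression is treated as not evaluable for that visit. It is neither a PD event nor a responder assessment. It does not count toward the two consecutive responder assessments, nor toward the rule that censors after two or more NE or missing assessments.
- **(c)** An Indeterminate assessment with no later evaluable scan is never the last non-PD assessment. A subject without an event is censored at the previous evaluable non-PD assessment.

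A simpler rule, giving the Indeterminate visit the status of the later scan, should be avoided. If the repeat scan were PR, the progressing scan would become PR too. SAP 3.7.1 would then find two consecutive responder assessments from a single responding scan, creating a false confirmed response dated 4 to 6 weeks early.

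The SAP should also state how Indeterminate is stored in the case report form and mapped in the 3.7.1 table. The cost is a few lines of text and one derivation rule; no design change or extra scans are needed.
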